#### **10.1.7. Source Documents**

All subject information recorded in the eCRF will be attributable to source data from the study site.

The investigator shall retain and preserve one copy of all data collected or databases generated in the course of the study, specifically including but not limited to those defined by GCP as essential. Essential documents should be retained until at least 2 years after the last approval of a marketing application in an ICH region and until there are no pending or contemplated marketing applications in an ICH region or at least 2 years have elapsed since the formal discontinuation of clinical development of the investigational medicinal product. These documents should be retained for a longer period, however, if required by the applicable regulatory requirements or by an agreement with the sponsor. It is the responsibility of the sponsor to inform the investigator/institution as to when these documents no longer need to be retained. Prior to destruction of any study essential documents, the investigator must first obtain written approval from the sponsor.

#### **10.1.8. Study and Site Closure**

The sponsor may suspend or terminate the study or part of the study at any time for any reason. If the investigator suspends or terminates the study, the investigator will promptly inform the sponsor and the IRB/IEC and provide them with a detailed written explanation. Upon study completion, the investigator will provide the sponsor, IRB/IEC, and regulatory agency with final reports and summaries as required by regulations. Study termination and follow-up will be performed in compliance with the sponsor or designee standard operating procedures.

The sponsor, investigator, or local and national regulatory authorities may discover conditions during the study that indicate that the study or study site should be terminated. This action may be taken after appropriate consultation between the sponsor and investigator.

Conditions that may warrant termination of the study/study site include, but are not limited to:

- The discovery of an unexpected, serious, or unacceptable risk to the subjects enrolled in the study.

- The decision on the part of the sponsor to suspend or discontinue testing or evaluation of the study treatment.
- Failure of the investigator to enroll subjects into the study at an acceptable rate.
- Failure of the investigator to comply with pertinent regulations.
- Submission of knowingly false information from the study site to the sponsor, study monitor, or local and national regulatory authorities.
- Insufficient adherence to protocol requirements.

**10.1.9. Publication Policy**

The sponsor's decision to publish or otherwise publicly communicate the results of this study will be made in accordance with all applicable laws, regulations, and sponsor policies regarding publication and communication of clinical study results.

Terms and provisions of the investigator's publication rights are governed by the Publication Section in the Clinical Trial Agreement.

## 10.2. Clinical Laboratory Tests

Serum Biochemistry	
Alanine aminotransferase	Creatinine
Albumin (total)	Gammaglutamyltransferase
Alkaline phosphatase	Phosphorus
Aspartate aminotransferase	Lactate dehydrogenase
Bicarbonate (or CO  )	Potassium
Bilirubin (total, conjugated [direct], and unconjugated [indirect])	Protein (total)
Blood urea nitrogen	Serum glucose
Calcium	Sodium
Chloride	Uric acid
Hematology	
Absolute differential count (neutrophils, lymphocytes, monocytes, eosinophils, basophils)	
Hematocrit	Platelet count
Hemoglobin	Red blood cell count
Mean corpuscular hemoglobin	Reticulocyte count
Mean corpuscular hemoglobin concentration	White blood cell count
Prothrombin time/INR	Mean corpuscular volume
Urinalysis	
Blood	pH
Glucose	Protein
Ketones	Specific gravity
Leukocyte esterase	Nitrites
Other Analyses	
Serum pregnancy tests (females)	FSH test (required for postmenopausal women)
Urine pregnancy test (females of childbearing potential)	
Serology	
Hepatitis B surface antigen	Hepatitis B core antibody
HIV	Hepatitis C virus (HCV) antibody
HCV polymerase chain reaction testing will be performed only for subjects positive for HCV.	
Urine Drugs of Abuse and Alcohol Screen (local laboratory only)	
Amphetamines	Alcohol
Barbiturates	Methadone (at screening only)
Benzodiazepines	Opiates
Cannabinoids	Cocaine

---

### **10.3. Adverse Events: Definitions and Procedures for Recording, Evaluating, Follow-Up and Reporting**

#### **10.3.1. Safety**

For safety information about MNK6106, refer to the most recent version of the Investigator's Brochure.

#### **10.3.2. Definitions**

##### ***Adverse Event***

An AE is any untoward or undesirable medical occurrence in a subject who is administered a study treatment, which does not necessarily have to have a causal relationship with this treatment. Examples of AEs include but are not limited to:

- Clinically significant laboratory findings.
- Clinically significant changes in physical examination findings.
- An AE occurring due to study treatment overdose whether accidental or intentional.
- An AE occurring from study treatment abuse.
- An AE associated with study treatment withdrawal.
- Unexpected AE.

An unexpected AE is defined as an AE, the nature and severity of which is not consistent with the applicable product information in the most recent version of the Investigator's Brochure.

##### **Serious Adverse Event**

An SAE is defined as any untoward medical occurrence that at any dose results in any of the following outcomes:

- Death.
- Life-threatening AE.
- Inpatient hospitalization or prolongation of existing hospitalization.
- A persistent or significant incapacity or substantial disruption of the ability to conduct normal life functions.
- Results in a congenital anomaly/birth defect.
- Other serious (important medical events).

##### ***Death***

Death is an outcome of an event. The cause of death should be recorded and reported on the SAE form. All causes of death must be reported as SAEs. The investigator should make every effort to

---

obtain and send death certificates and autopsy reports to the sponsor or designee, or state not available.

### ***Life-Threatening Event***

An AE or suspected adverse reaction is considered "life-threatening" if, in the view of either the investigator or sponsor, its occurrence places the subject at immediate risk of death. It does not include an AE or suspected adverse reaction that, had it occurred in a more severe form, might have caused death. For example, hepatitis that resolved without evidence of hepatic failure would not be considered life threatening, even though hepatitis of a more severe nature can be fatal. Similarly, an allergic reaction resulting in angioedema of the face would not be life threatening, even though angioedema of the larynx, allergic bronchospasm, or anaphylaxis can be fatal.

### ***Hospitalization***

Hospitalization is defined as an official admission to a hospital. Hospitalization or prolongation of a hospitalization constitutes a criterion for an AE to be serious. The following situations should not be reported as SAEs:

- A hospitalization or prolongation of hospitalization is needed for a procedure required by the protocol.
- A hospitalization or prolongation of hospitalization is part of a routine procedure followed by the center (eg, stent removal after surgery). This should be recorded in the study file.
- A hospitalization for a pre-existing condition that has not worsened.

### ***Important Medical Events***

Important medical events that may not result in death, be life threatening, or require hospitalization may be considered serious when, based upon appropriate medical judgment, may jeopardize the subject and may require medical or surgical intervention to prevent one of the outcomes listed above. Examples of such medical events include allergic bronchospasm requiring intensive treatment in an emergency department or at home, blood dyscrasias or convulsions that do not result in inpatient hospitalization, or the development of drug dependency or drug abuse.

AEs (serious or non-serious) that commonly occur in the study population or background regimen will be considered anticipated events. Such events include known consequences of the condition under investigation (eg, symptoms, disease progression) and other events that may be common in this study population. Anticipated events are to be recorded on the eCRF and reported as SAEs when serious. These SAEs will not be expedited to health authorities, but rather, included in aggregate safety reports.

### 10.3.3. Adverse Event and Serious Adverse Event Classifications

The descriptions and grading scales found in CTCAE v5.0 ([U.S. HHS CTCAE Version 5.0, 2017](#)) will be utilized for AE reporting.

#### *Study Drug Relatedness*

The following classifications should be used when evaluating the relationship of AEs or SAEs to study treatment ([Table 3](#)).

**Table 3: Adverse Event Relationships**

Relationship	Definition
Not Related	No relationship between the AE and the administration of study treatment; the AE cannot be explained by other etiologies such as concomitant medications or subject's clinical state.
Unlikely Related	The current state of knowledge indicates that a relationship to study treatment is unlikely.
Possibly Related	An AE that follows a plausible temporal sequence from administration of the study treatment to the start of the AE and follows a known response pattern to the suspected study treatment. The reaction might have been caused by the subject's clinical state or concomitant medications.
Related	The AE that follows a plausible temporal sequence from administration of the study treatment to the start of the AE and follows a known response pattern to the study treatment. The suspected causality can be confirmed with a positive re-challenge test or supporting laboratory data.

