### **7.1. Discontinuation of Study Treatment**

Subjects who discontinue, or are withdrawn from study treatment for any reason, will be encouraged to complete the final visit and provide any additional follow-up information as required by the study, unless the subject specifically indicates that they will not participate in any further evaluations.

Permanent study treatment discontinuation is required for any of the following:

- A 'serious' adverse reaction (ie, an SAE considered at least possibly related to the study treatment administration) in 1 subject.
  - Grade 4 AEs as per Common Terminology Criteria for AEs (CTCAE) v5.0 that are not expected in the context of underlying medical conditions.
  - The investigator considers study treatment discontinuation to be in the subject's best interest for any other reason.
  - Major protocol violation.
  - Symptoms of an intercurrent illness not consistent with the protocol requirements or that justify withdrawal.
-

- The subject becomes pregnant.

Discontinuation of study treatment for abnormal liver function should be considered by the investigator when a subject meets one of the conditions outlined in Section 10.5.

Additional reasons for permanent study treatment discontinuation include, but are not limited to, the following:

- Subject/caregiver withdraws consent to receive study treatment.
- Death.

If a clinically significant cardiac finding is identified (including but not limited to changes from baseline in QTcF) after the start of study treatment, the investigator or a qualified designee will determine if the subject can continue in the study and if any change in management is needed.

The reason for study treatment discontinuation will be recorded.

No dose modifications or temporary treatment discontinuations are permitted in this study.

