### 9.5.1. Safety Analyses

For safety variables, 2 observation periods are defined:

- The pretreatment period is defined as the time from signing the ICF until administration of the first dose of study drug.

- The treatment-emergent period is defined as the time from administration of the first dose of study drug to the end of the study.

Treatment-emergent AEs are defined as those that are not present at start of study drug dosing or that represent the exacerbation of a pre-existing condition during the treatment-emergent period.

AEs will be coded using the Medical Dictionary for Regulatory Activities (MedDRA) by preferred term within system organ class. The number of AEs and the number of subjects reporting AEs will be listed and summarized descriptively by body system, preferred term, severity, and causality for each treatment group. Both pretreatment and treatment-emergent AEs (events that are new in onset or aggravated in severity following treatment) will be included in all summaries. SAEs (including death) will be summarized. Treatment-emergent AEs leading to permanent treatment discontinuation will be listed and summarized by treatment group.

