**Table 4: Adverse Event Severity Grades**

Grade	Definition
Grade 1	Mild AE
Grade 2	Moderate AE
Grade 3	Severe AE
Grade 4	Life-threatening AE
Grade 5	Death

Not all grades are appropriate for all AEs. In particular, Grade 5 (Death) is not appropriate for all AEs and therefore will not be considered an option for grading severity of AEs; instead, death, if it occurs, should be recorded as the outcome of a serious AE.

To ensure there is no confusion or misunderstanding of the difference between the terms “serious” and “severe,” which are not synonymous, the following note of clarification is provided:

The term “severe” is used to describe the intensity (severity) of a specific event (as in mild, moderate, or severe myocardial infarction); the event itself, however, may be of relatively minor medical importance (such as a severe headache). This is not the same as “serious,” which is based on the subject/event outcome or action criteria usually associated with events that pose a threat to a subject's life or functioning. Seriousness (not severity) serves as a guide for defining regulatory reporting obligations.

If an AE increases in severity (eg, from moderate to severe); decreases in severity (eg, changes from moderate to mild); or if there is a change in seriousness, a new AE will be opened, and the original AE will be closed. If an AE is still ongoing at the time of a subject’s completion of the Final Visit, the resolution/stop date and time is left blank.

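### Table 3 reverses a clause of the Not Related definition, and AEs split at each severity change have no count-once rule in the protocol text

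*Combined protocol and SAP*

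**What the plan says.** **Relationship categories.** Table 3 in Section 10.3.3 gives the categories that investigators should use. Not Related reads "No relationship between the AE and the administration of study treatment; the AE cannot be explained by other etiologies such as concomitant medications", and the sentence goes on to name the subject's clinical state as well. Unlikely Related reads "The current state of knowledge indicates that a relationship to study treatment is unlikely", with no condition about other causes. Possibly Related asks for a plausible time sequence and a known response pattern, and adds: "The reaction might have been caused by the subject's clinical state or concomitant medications".

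**Disease-related events.** Section 10.3.2 (Important Medical Events) treats consequences of the underlying disease as anticipated events and still requires them to be captured: "Anticipated events are to be recorded on the eCRF and reported as SAEs when serious".

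**Record splitting.** The text under Table 4 closes the original AE and starts another when severity rises, and likewise when it "decreases in severity (eg, changes from moderate to mild); or if there is a change in seriousness, a new AE will be opened".

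**Analysis.** Section 9.5.1 states: "The number of AEs and the number of subjects reporting AEs will be listed and summarized descriptively by body system, preferred term, severity", and also by causality, for each treatment group. It defines a pretreatment and a treatment-emergent period, then places both kinds of AE in every summary. Section 9.5.2 leaves the exposure time periods to a statistical analysis plan that is not reproduced in the combined document.

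**The concern.** AEs and SAEs are the endpoint for the first secondary objective (Section 3.2), and no hypothesis is tested (Section 9.3). The descriptive AE tables are therefore the safety result of the trial, with 48/4 = 12 subjects planned per arm.

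A reversed definition affects data at the point of entry. The investigator chooses the category at the site, and no later analysis plan can recover what would have been chosen under a correct definition.

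The splitting rule affects counting. If every record counts as an AE, the number of AEs depends on how often events change grade as well as on how many events occur, and one subject can appear in several severity or causality rows.

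The display of pretreatment AEs is a smaller matter. Section 9.5.1 does not say outright that they are shown apart from treatment-emergent ones.

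**Working it through.** **(a) The Not Related clause.** Take an AE that the investigator attributes to cirrhosis and not to study drug.

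1. Not Related, first clause (no relationship to treatment): met.
2. Not Related, second clause (no other etiology explains the AE): not met, because the clinical state does explain it. Read literally, the AE fails the category.
3. Unlikely Related: nothing in the definition excludes it, so this is the most natural place for it to fall.
4. Possibly Related: needs a plausible time sequence and a known response pattern to study treatment. An AE that meets these conditions meets them however Not Related is worded.

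The absence of another explanation is a reason to suspect the drug, so the clause works against its own category. The Possibly Related row treats the same two factors, clinical state and concomitant medication, as alternatives to a drug cause. Disease-related AEs must be recorded, so such cases will occur.

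Section 7.1 requires permanent discontinuation for "an SAE considered at least possibly related to the study treatment administration". Not Related and Unlikely Related both lie below that line, so movement between them does not alter it.

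**(b) Counting split records.** Inputs: the rule under Table 4 and the tabulation in Section 9.5.1. The documents give no figure to reproduce. For one episode in one subject, records = 1 + number of changes in severity or seriousness.

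| Course of one episode | AEs counted | Severity rows | Subjects with an AE |
|---|---|---|---|
| moderate, mild | 1 + 1 = 2 | 2 | 1 |
| mild, moderate, mild | 1 + 2 = 3 | 2 | 1 |
| severe, moderate, mild | 1 + 2 = 3 | 3 | 1 |
| any course, counted once at worst severity | 1 | 1 | 1 |

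Across a trial, AEs counted per true episode = 1 + f × k, where f is the share of episodes that change and k is the number of changes in each of those. The documents give neither. Assuming f from 10% to 50% and k from 1 to 3, the range is 1 + 0.10 × 1 = 1.1 to 1 + 0.50 × 3 = 2.5. This shows how the rule behaves; it is not a forecast. One subject is 1/12 = 8.3 percentage points of an arm, so an extra appearance in a severity row is visible.

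**(c) Display by period.** Section 9.5.1 defines two periods for safety variables, includes both kinds of AE in all summaries, and names only treatment-emergent AEs for the summary of events leading to permanent discontinuation. The two periods imply separate display, but no sentence says so.

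**The case against.** The strongest case on the other side has four parts.

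*The first clause governs.* An investigator who sees no relationship can choose Not Related and ignore the second clause. Many may do so, which limits the effect. The table still asks for something that its own category should not require, and investigators may resolve this differently.

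*Counting rules belong in a SAP.* This is fair. Maximum-severity and count-once conventions are ordinary SAP content, and a separate SAP may already contain them. What can be said is that the available text has none. A SAP could settle (b) and (c), but not the wording of Table 3.

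*The study is exploratory, and subject counts are safe.* The number of subjects with any AE is indeed unaffected by splitting. Event counts, and subject counts by severity or causality, are not protected.

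*A mid-study change leaves causality judged under two wordings.* This stands. The Amendment 3 summary refers to investigator input during the trial, so the study is already running, and the fix has to allow for it.

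A reader might also draw stronger conclusions that the documents do not support:

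- That unexplained AEs are pushed into Not Related and drug reactions hidden. The first clause still requires no relationship to treatment.
- That the discontinuation criterion in Section 7.1 is distorted. Both affected categories are below its threshold.
- That an AE improving after the first dose is wrongly flagged as treatment-emergent because its new record starts after dosing. Section 9.5.1 requires a new event or a worsening.
- That onset or duration of AEs of special interest is lost. Section 10.3.5 provides a dedicated eCRF page and narratives.
- That pretreatment AEs will be pooled with treatment-emergent ones. The two defined periods, and the Amendment 1 summary (item 31), point to display by period.

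**Conclusion.** Part (a) is wrong as written. Its effect is limited to the Not Related/Unlikely Related split in a descriptive table. That disease-explained AEs would move to Unlikely Related rests on investigators reading the definition literally.

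Part (b) is an omission in the available text. Followed literally, a three-stage episode counts as 3 AEs and can occupy 3 severity rows for 1 subject. The total effect depends on how often AEs change grade, which the documents do not give, and there is no effect if a separate SAP already has a count-once rule.

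Part (c) is a request for clarification only.

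Taken together this is a minor point: no test, primary result or discontinuation threshold is affected.

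**What to change.** **(a) Table 3.** Reword the second clause of Not Related so that the AE can be explained by other etiologies, without making another etiology a requirement. Record the date of the change. Present Not Related and Unlikely Related combined as well as separately, so that AEs judged under the two wordings stay comparable. Cost: one clause, but it needs a protocol amendment and IRB/IEC approval (Section 10.1.1). The separate categories will still mix two wordings.

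**(b) Section 9.5.1 or the SAP.** Keep every record and link consecutive records of the same event at the analysis stage. Count each episode once, at its worst severity, as serious if any linked record is serious, and at its strongest relationship. Count each subject once per preferred term on the same basis. In treatment-emergent tables, apply the existing definition and use only the maximum reached after the first dose. Cost: some programming, review of which records belong together, and lower raw event counts. No safety data are lost. If a SAP already holds an equivalent rule, a cross-reference is enough.

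**(c) Section 9.5.1.** Add one sentence saying that pretreatment and treatment-emergent AEs are tabulated separately. Cost: negligible.

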### **2.1.2. Clinical Safety Data**

Safety data from completed sponsor and investigator-initiated clinical studies demonstrated that a single IV dose of 20 g L-Ornithine phenylacetate IV solution (MNK6105) infused over 4 hours or daily 20 g IV doses infused over 24 hours for up to 5 days, were generally well tolerated.

Regarding oral administration with MNK6106 (L-Ornithine phenylacetate tablets), Study OCR002-SP103 was an open-label Phase 1/2a, 2-part crossover study in 30 adult subjects with varying degrees of cirrhosis, who received oral administration of MNK6106. The safety conclusions were that MNK6106 was safe and well-tolerated when administered at doses up to 21 g/day for 5 days. There were no deaths, 1 serious adverse event (SAE) was reported during Part 2 of the study (SAE of urinary tract infection in a subject while receiving 21 g/day; the event was considered not related to study drug treatment). In addition, safety data from completed Phase 1/2a clinical studies with a single IV dose of 5 g given as an oral solution, as well as oral administration of MNK6106 tablets (6 g, 12 g, and 21 g per day for 3 periods, 5 days per period with a minimum 4-day washout in between) indicate that both IV and oral administration of L-

---

Ornithine phenylacetate were generally well tolerated. No Phase 2/3 studies of MNK6106 have been initiated.

A detailed description of the chemistry, pharmacology, efficacy, and safety of L-Ornithine phenylacetate is provided in the Investigator's Brochure ([Mallinckrodt, 2019](#)).

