#### 10.3.4. Adverse Event and Serious Adverse Event Recording and Reporting

AEs and SAEs will be recorded from signing of the ICF through completion of the final visit. The investigator is required to record the AE or SAE regardless of the severity of the event or its relationship to study treatment. The investigator must follow up on all AEs and SAEs reported to have occurred through the final visit until the event has resolved or stabilized or at such time the investigator refers the subject to a nonstudy physician. The investigator will document the further follow-up information in the subject’s source document.

During the period specified above, the investigator will:

- Record all AEs and SAEs from the signing of the ICF through the completion of the final visit.
- Report all SAEs on an SAE Report Form to Mallinckrodt Global Pharmacovigilance or designee.
- Report all pregnancies to Mallinckrodt Global Pharmacovigilance or designee on the appropriate form.
- Submit any Expedited Safety Report or Suspected Unexpected Serious Adverse Reaction from Mallinckrodt Global Pharmacovigilance or designee to the IRB/IEC.

The reporting requirements for AEs are summarized in [Table 5](#).

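### Table 3 makes a known response pattern a condition of both positive causality ratings, so a reaction of a new kind to MNK6106 with plausible timing fits neither

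*Combined protocol and SAP*

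**What the plan says.** Section 10.3.3 (Study Drug Relatedness) directs that Table 3 be used to rate the relationship of all AEs and SAEs to study treatment. The documents contain no other causality scale. Its four categories read as follows.

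- *Possibly Related*: plausible timing after dosing, and the event "follows a known response pattern to the suspected study treatment". A second sentence allows that clinical state or concomitant medication might have been the cause.
- *Related*: the same timing condition, and the event "follows a known response pattern to the study treatment. The suspected causality can be confirmed" by re-challenge or laboratory data.
- *Unlikely Related*: "The current state of knowledge indicates that a relationship to study treatment is unlikely".
- *Not Related*: no relationship to study treatment, with the added statement that "the AE cannot be explained by other etiologies such as concomitant medications or subject's clinical state".

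Other parts of the protocol use these ratings or the idea of unexpectedness:

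- Section 7.1 lists first, among the criteria that require permanent discontinuation, "an SAE considered at least possibly related to the study treatment administration".
- Section 10.3.2 defines an unexpected AE as one "the nature and severity of which is not consistent with the applicable product information in the most recent version of the Investigator's Brochure".
- Section 10.3.4 gives the investigator the task "Submit any Expedited Safety Report or Suspected Unexpected Serious Adverse Reaction", passing material from sponsor pharmacovigilance to the IRB/IEC.
- Section 9.5.1 summarises AEs by causality, among other factors, for each treatment group.

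**The concern.** A causality scale in early development has to be able to register a reaction that nobody has seen before. This one makes prior knowledge of the reaction a condition of calling it even possibly related.

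That matters here because experience with the tablets is limited. Section 2.1.2 describes one tablet study in 30 subjects and states "No Phase 2/3 studies of MNK6106 have been initiated". Safety and tolerability is the first secondary objective (Section 3.2), and Section 4.2 describes the trial as a dose-ranging safety study. At stake are the related-AE and related-SAE counts by arm and one mandatory discontinuation criterion that depends on the rating. The sponsor's recognition of a suspected unexpected reaction may also suffer, if it relies on the investigator's rating.

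**Working it through.** The plan gives no figure to reproduce; the check sets the definitions side by side. Take an SAE in an MNK6106 subject that has plausible timing after dosing and is of a kind not previously known for the drug.

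**Step 1: which category fits?**

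| Category | What it needs | Met? |
|---|---|---|
| Related | timing and known pattern | No: pattern fails |
| Possibly Related | timing and known pattern | No: pattern fails |
| Unlikely Related | present knowledge points against a relationship | Not clearly: having no knowledge is not evidence against |
| Not Related | no relationship | Not clearly: plausible timing leaves the question open |

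The two conditions in *Possibly Related* are joined by an *and*, and the sentence about alternative causes does not loosen it. The last row is harder to apply because of the clause in Table 3 that other causes cannot explain the event. That clause seems to run opposite to what the category name suggests. The test event is therefore shut out of the positive categories and has no clear home in the others.

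**Step 2: Section 7.1.** The first criterion needs a rating of *Possibly Related* or higher. From step 1 that rating is unavailable, so on a literal reading the criterion does not fire. Three routes need no relatedness rating: Grade 4 AEs not expected from the underlying conditions (7.1), the investigator's view of the subject's best interest (7.1), and an AE judged an unacceptable risk by the investigator, sponsor or medical monitor (7.2).

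**Step 3: unexpected events.** Section 10.3.2 refers to both nature and severity. An event new in nature cannot readily follow a known pattern as well. An event of a known kind, but more severe than the Investigator's Brochure describes, can meet the pattern condition, be rated *Possibly Related*, and arguably still be unexpected. The gap therefore concerns reactions new in nature.

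**Step 4: reporting.** Section 10.3.4 requires AEs and SAEs to be recorded regardless of relationship and all SAEs to be reported to sponsor pharmacovigilance. Table 5 sets 24 hours from first knowledge for all serious events. Suspected unexpected serious reactions come from the sponsor, and the investigator forwards them. The documents describe no separate sponsor causality assessment or scale.

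**Step 5: size in the summaries.** 48 subjects / 4 arms = 12 per arm; 3 MNK6106 arms × 12 = 36. One SAE of the test kind is 1/12 = 8.3% of its arm and 1/36 = 2.8% of MNK6106 subjects.

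- SAE count: 1 under either wording.
- Related-SAE count: 1 if *Possibly Related* were available; 0 on the literal wording.

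The documents give no expected rate of new reactions, so no expected under-count can be calculated.

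**The case against.** The strongest reply is that this is a drafting gap which clinical judgment will fill, and that little depends on it. Several parts of that reply stand, and they rule out stronger readings.

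- *The rules cannot work for any unexpected event.* A reader might infer this, but an event unexpected only in severity can still be rated possibly related. Table 3 also does not tie a known pattern to the Investigator's Brochure.
- *Such an event would never become a suspected unexpected serious adverse reaction.* The documents do not say that the investigator's Table 3 rating settles that status. The sponsor receives every SAE and issues these reports under procedures not shown here.
- *Every such event is forced down to unlikely or not related.* Table 3 does not clearly place it there; it leaves it unplaced.
- *Subjects are left unprotected.* The routes in Sections 7.1 and 7.2 that need no relatedness rating remain, and Section 10.1.8 allows termination for an unexpected serious risk.
- *The arm comparison is biased in favour of MNK6106.* This would need a rifaximin adverse event profile, and the documents give none. No direction of bias can be shown.

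It is also fair to say that some patterns are already known: Sections 2.1.2 to 2.3 cite intravenous studies of the same entity and list phenylacetate effects. AEs are also summarised by preferred term and severity, SAEs are summarised whatever their cause, and special-interest events get narratives without a causality condition (10.3.5).

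This narrows the gap without closing it. The special-interest list covers CNS and abuse-related events, so a new reaction outside those groups gains nothing from it. Routes that protect the individual subject do not correct the causality data. For a new kind of SAE below Grade 4, the remaining routes rest on judgment.

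**Conclusion.** The point holds as a defect in one definition with limited but real consequences. As written, an AE that is new in nature for MNK6106 and has plausible timing meets neither positive category, and no other category clearly covers it. The Section 9.5.1 causality summaries would under-count related new reactions, and the related-SAE criterion in Section 7.1 would not fire for them. Identification of suspected unexpected serious reactions may be impaired, but it is not disabled.

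This rests on two assumptions: that investigators apply Table 3 as worded, and that no separate guidance relaxes it. The documents contain none. If investigators read the pattern condition loosely, the under-count shrinks, but ratings may then differ between investigators. Any single event changes one cell of the causality table; its appearance in the AE and SAE listings is unaffected.

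**What to change.** In Table 3, define *Possibly Related* as a plausible temporal sequence together with a reasonable possibility that study treatment caused the event, and state that a known response pattern supports the rating but is not required. The sentence on alternative causes can stay. Align the eCRF completion guideline.

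Reconcile the revised Table 3 with Sections 7.1, 10.3.2 and 10.3.4, so that the rating, the discontinuation criterion that uses it, the definition of an unexpected event and the reporting route fit together. State whether the sponsor assesses causality independently of the investigator and on what scale. Check the second clause of *Not Related* in the same edit. No change to the discontinuation rule is proposed here, and no view on it is taken.

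The cost is one table cell and the matching guideline text. The downside is that somewhat more events will be rated possibly related.
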